15 VULNERABLE POPULATION

15.1 This clinical investigation will be conducted on adult populations only. No vulnerable populations such as children and/or pregnant females etc. will be included in the study population.

16 EARLY TERMINATION OR SUSPENSION OF THE CLINICAL INVESTIGATION

Suspension or Premature Termination	
Grounds for suspension or premature termination of the clinical investigation include but are not limited to:
 
Non compliance of the investigational site personnel to the CIP and or investigational procedures
 
Severe Adverse Events that demonstrate danger to the patient population
 
Unethical performance on the part of any of the investigators
 
Device Adverse Effects that demonstrate danger to the patient population or severe flaw in investigational device design
 
Failed audit of investigation with serious flaws to study design,

--	--

Clinical Investigational Plan			
Protocol ID	934CLD	Sponsor	GI View Ltd.
Revision	03	Investigational Device	Aer-O-Scope® Colonoscope System

	
performance or outcomes
 
Business/Financial issues that cannot be resolved
 
Other unforeseen events that give the PI/Sponsor reasonable doubts to the safety and/or performance of the system which will be referred to the Data Safety Monitoring Committee for review prior to determination of suspension or termination.

Blinding/Masking Technique	This clinical investigation does not include any blinding or masking.
Follow-Up	Patients will be followed up 24-48 hours post procedure via telephone by the clinical coordinator at each site. Patients who undergo therapeutic interventions will only be terminated from the study upon receiving the histology results.

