	
It should be noted that the expected number of advanced adenomas will be significantly lower than the number of polyps and the number of adenomas. The evaluation of this objective will most likely not reach statistical significance due to the small expected sample size of advanced adenomas.
 
2.3. To define and document the learning curve for the operation of the Aer-O-Scope Colonoscope System and use of therapeutic access using the Aer-O-Scope Colonoscope System – Using a 5 point Likert Scale (for perceived physician proficiency). The first ten (10) cases will be training for system operation. The first twenty (20) therapeutic interventions per physician will be training for therapeutic access.
 
2.4. Colonoscopy timing for both Aer-O-Scope and conventional colonoscopy will be documented for the following properties:
 
2.4.1. Cecal intubation time (not including therapeutic intervention times)
 
2.4.2. Withdrawal time (not including therapeutic intervention times)
 
2.4.3. Total procedure time (not including therapeutic intervention times)
 
3. Tertiary Objectives:
 
3.1. Timing of therapeutic interventions (see Appendix 3: Therapeutic Accessories Used in This Study) performed with the Aer-O-Scope Colonoscope System will be documented for the purpose of data collection only

Study Endpoints	
1. Primary
 
1.1. Adenoma miss rates (AMR) for each study cohort
 
1.2. No serious adverse events or serious adverse device effects using the Aer-O-Scope Colonoscope System.
 
2. Secondary
 
2.1. Polyp miss rates (PMR) for each study cohort
 
2.2. Advanced adenoma miss rates (AAMR) for each study cohort
 
2.3. Perceived proficiency in Aer-O-Scope operation, mean Likert score between 1-3.
 
2.4. Cecal intubation time (not including therapeutic intervention times)
 
2.5. Withdrawal times (not including therapeutic intervention times)
 
2.6. Total procedure time (not including therapeutic intervention times)
 
3. Tertiary
 
3.1. Therapeutic intervention metrics (time, tool, success rate)

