Medical Procedure	
The Aer-O-Scope Disposable Scanner like any conventional colonoscope is inserted into the rectum and then maneuvered to the cecum. The Aer-O-Scope has an incorporated propulsion system to advance the optical imaging head through the colon. The propulsion system utilizes soft pliable balloons and CO₂ gas to gently propel the optical imaging head inwards on intubation and outwards upon retraction. The operator gently eases the multi-luminal cable inward towards the cecum during the insertion phase and gently pulls the cable during retraction scan phase both while steering the optical imaging head with the ergonomic joystick.
 
If pathology of any type is detected during the procedure, a standard therapeutic accessory (at least 230cm in length and ≤1.8mm in diameter) is inserted through one of the Aer-O-Scope two (2) working channels (2.1mm diameter each) and the polyp is removed or biopsied. In the event that the pathology cannot be removed due to size, shape and/or location, the area adjacent to the pathology is tattooed to mark for later therapeutic intervention.
 
In this study, subjects will undergo tandem colonoscopy with the Aer-O-Scope Colonoscope System and a conventional colonoscope (see Appendix 2: Conventional Colonoscopes Used in this Investigation). Subjects will be randomized in blocks to begin either with the Aer-O-Scope Colonoscope System or with the conventional colonoscope. The same endoscopist will perform both procedures. Because the physicians will see which device they are using to perform the colonoscopies, blinding will not be possible.
 
Each subject will undergo colonoscopy in tandem with each device. All pathologies will be removed (or tattooed) during the procedures.
 
Data will be documented on Case Report Forms (973CLD). Data related to adenomas will be retrieved from histology reports.

Clinical Investigational Plan			
Protocol ID	934CLD	Sponsor	GI View Ltd.
Revision	03	Investigational Device	Aer-O-Scope® Colonoscope System

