6 DESIGN OF THE CLINICAL INVESTIGATION

6.1 General

This will be a prospective multi-center, multi-national comparative non-blinded clinical investigation. Each subject will undergo back-to-back tandem colonoscopies with the Aer-O-Scope Colonoscope System and a conventional colonoscope (for a list of scopes to be used, see Appendix 2) since this is a tandem colonoscopy study, each subject will serve as their own control. The 1st procedure will be randomized, half to Aer-O-Scope Colonoscope System and half to conventional colonoscope. The same investigator will perform both procedures on each subject. All pathologies found will be either removed or tattooed. Unmarked pathologies found on second pass will represent those missed during the 1st pass, thus making the subject and the control one and the same. Tattooed pathologies that can be removed endoscopically will be removed in an additional colonoscopy. This may occur if a large polyp cannot be removed for any reason with the Aer-O-Scope, but can be removed with conventional colonoscopy.

Subjects will be randomized in blocks of twenty (20) for either Aer-O-Scope or conventional colonoscopy as the first procedure. Physicians will be notified of the procedural order immediately prior to first colonoscopy. Up to the first ten (10) cases for each physician (system operation training cases) will all begin with the Aer-O-Scope colonoscopy as the first procedure.

The primary endpoint of AMR was chosen as this measure appears to be related to the performance of colonoscopy and reduction in colorectal cancer incidence. During the course of the last decade, several major visualizations studies have been performed and it has become common practice to use the “second-pass” method for measuring colonoscopy visualization methods^{iii,iv}. In the “second-pass” method, during the course of the first colonoscopy, all visualized lesions are removed (or tattooed in the event that they cannot be removed for any reason.). Any unmarked abnormalities discovered during the second pass colonoscopy are considered to be missed pathologies for the first pass colonoscopy.

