6.2 Investigational Device(s) and Comparator(s)

Each subject will undergo back-to-back tandem colonoscopies, which could last approximately up to one (1) hour each. It is possible that procedures that have multiple therapeutic interventions may go beyond the expected time frames.

The Aer-O-Scope Colonoscope System will be compared to standard conventional colonoscopes that are normally used at the study sites (see Appendix 2 for the exact scope models). This study is intended to compare visualization properties of the currently used technologies; therefore, the standard colonoscope was chosen as the comparator.

During the course of this investigation, subjects will undergo the standard (split) bowel preparation used for colonoscopy at the clinic. This may include but may not be limited to one of the following medications:

- Moviprep
- Picolax
- Miralax
- Motilium
- Laxadine
- Golytely

During the course of this investigation, subjects will undergo the standard sedation given for colonoscopy. This may include but is not limited to the following medications:

- Biatryl/Fentanyl
- Dormicum/Medazolam
- Propofol

Clinical Investigational Plan			
Protocol ID	934CLD	Sponsor	GI View Ltd.
Revision	03	Investigational Device	Aer-O-Scope® Colonoscope System

During the course of this investigation, subjects who have findings during their colonoscopies will undergo polypectomies and/or biopsies and/or tattooing using standard therapeutic tools. This may include but is not limited to the following therapeutic tools and medications:

Biopsy forceps – both hot and cold

- Snare – both hot and cold
- Needle – for tattooing or injecting
- Saline solution
- Tattooing ink
- Epinephrine
- Argon plasma coagulation
- Cautery forceps/needles

The number of polyps detected during the second pass colonoscopy (that were not removed or tattooed during the first pass) will represent the overall number of missed polyps for the first colonoscopy. The number of detected polyps is defined as the number of polyps detected during colonoscopy. Each polyp removed (regardless of first or second pass colonoscopy) will be sent to histology as a singular specimen. Histology will determine if the lesion removed is an adenoma, hyperplastic polyp, serrated adenoma, cancer etc.

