Patients with polyps ≥ 20 mm detected during 1st pass with conventional colonoscopy will be withdrawn from the study. Patients with polyps ≥ 20 mm detected during 1st pass with the Aer-O-Scope[®] will be tattooed for polyp resection during the 2nd pass with a conventional colonoscope.

Patients with polyps ≥ 20 mm that were missed during a 1st pass with a conventional colonoscope and detected with the Aer-O-Scope will be tattooed and undergo a 3rd pass with a conventional colonoscope for polypectomy/EMR (endoscopic mucosal resection).

Upon determination of polyp histology, the NMA will be calculated for each procedure. The NMA is defined as the number of adenomas detected during the second pass colonoscopy and confirmed histologically, that were not removed (or tattooed) during the first pass colonoscopy. The NMA will be calculated for both cohorts alike. The AMR will then be calculated for each cohort.

In the event pathology that is too large to remove or in a location preventing endoscopic removal is visualized during the course of any procedure, the pathology will be marked using tattooing. In the event a lesion is too large to remove during second pass colonoscopy with the Aer-O-Scope Colonoscope System but can be removed endoscopically with a conventional colonoscope, the pathology will be tattooed and the subject will undergo a third procedure with a conventional colonoscope using the same bowel prep and sedation, to remove the said pathology. Pathologies of this type will not be considered missed by the Aer-O-Scope.

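### The plan excludes all masking, but its stated reason covers only the endoscopist; the histology read that feeds the primary adenoma miss rate could be masked to device and pass and is not

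*Combined protocol and SAP*

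**What the plan says.** Section 16, in the row on blinding and masking, says "This clinical investigation does not include any blinding or masking", with no exception. Section 6.1 describes a "prospective multi-center, multi-national comparative non-blinded clinical investigation". The only justification is in Section 2, under Medical Procedure: "Because the physicians will see which device they are using to perform the colonoscopies, blinding will not be possible".

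The first primary endpoint in the synopsis (Section 1.5) is "Adenoma miss rates (AMR) for each study cohort", defined on histology. Three statements show how histology enters it:

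- Section 6.2: "Histology will determine if the lesion removed is an adenoma, hyperplastic polyp, serrated adenoma, cancer etc".
- Section 2: "Data related to adenomas will be retrieved from histology reports".
- Section 6.2: "Upon determination of polyp histology, the NMA will be calculated for each procedure". The AMR per cohort is calculated after that.

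Section 6.2 also says that each removed polyp, from either pass, "will be sent to histology as a singular specimen". The plan does not mention coded labels, a masked or central reader, or leaving device and pass off the pathology request.

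**The concern.** The reason for having no blinding applies to the person holding the colonoscope. The pathologist does not see the colonoscope, so the reason does not justify leaving the histology read open.

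The read matters because its effect on the AMR depends on the pass. A second-pass lesion called an adenoma enters both numerator and denominator of the first device's miss rate. A first-pass lesion enters only the denominator. A reader who knew that a lesion was found on the second pass, and by which device, could shift borderline calls in a direction that favours one device. Section 3 states that the study is intended to show a significantly lower miss rate for the sponsor's device, so an open read of the deciding variable would invite this criticism.

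**Working it through.** **Setting the statements side by side.** Section 16 excludes all masking. Section 2 gives a reason that covers the operator. Sections 2 and 6.2 make histology the arbiter of adenoma status and place the count of missed adenomas after it. So the exclusion is wider than its reason, and the part left unexplained bears on the primary endpoint.

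The plan states no figure on this point, so there is none to reproduce. The calculations below only show how much a few calls can matter.

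**Adenomas per cohort.** Section 7 gives 240 patients with 10% dropout allowed for, 50% of patients with adenomas, and 2 adenomas in each of those. Section 6.1 splits the order of procedures half and half.

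- Patients per cohort: 240/2 × 0.90 = 108.
- Adenomas per cohort: 108 × 0.50 × 2 = 108.

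**Test.** Section 7 specifies a two-sided Z-test for two proportions at 5%. I use the pooled form: z = (p2 − p1) / √[p(1 − p)(1/n1 + 1/n2)], where p is the pooled proportion. Cohort 1 is Aer-O-Scope first and cohort 2 is conventional first.

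**Assumed near-threshold case (counts chosen for illustration, not taken from the plan).**

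- 15/108 vs 25/108: difference 0.0926, pooled p = 40/216 = 0.1852, standard error 0.0529, z = 1.75, p = 0.080.
- Two more second-pass lesions in cohort 2 called adenoma, 15/108 vs 27/110: difference 0.1066, pooled p = 42/218 = 0.1927, standard error 0.0534, z = 1.99, p = 0.046.

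One such call near the plan's 25% moves the conventional AMR by 28/109 − 27/108 = 0.0069, about 0.7 percentage points.

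**About the plan's own effect (0.10 vs 0.25).** Here the calls are removed from cohort 2, to see how robust a positive result is.

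| Calls removed | Counts | z | p |
|---|---|---|---|
| 0 | 11/108 vs 27/108 | 2.86 | 0.004 |
| 2 | 11/108 vs 25/106 | 2.62 | 0.009 |
| 6 | 11/108 vs 21/102 | 2.10 | 0.036 |
| 7 | 11/108 vs 20/101 | 1.96 | 0.051 |

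Seven calls, all in one direction in one cohort, are needed before significance is lost.

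**False-positive rate under assumed biased reading.** Suppose the true AMR is 0.25 in both cohorts, with 108 adenomas each. Let second-pass lesions be called adenoma a fraction d less often in cohort 1 and d more often in cohort 2. The apparent AMR is then 0.25f / (0.25f + 0.75), with f = 1 − d or 1 + d.

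| d | Cohort 1 | Cohort 2 | Spurious difference | Two-sided rejection rate |
|---|---|---|---|---|
| 0 | 0.250 | 0.250 | 0 | 5% |
| 5% | 0.241 | 0.259 | 1.9 points | about 6% |
| 10% | 0.231 | 0.268 | 3.8 points | about 10% |
| 20% | 0.211 | 0.286 | 7.5 points | about 25% |

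The documents give no value for d. The range is an assumption.

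**The case against.** The strongest reply is that the harm is inferred. A reader might take the sentence in Section 16 to mean that pathologists will know device and pass. The documents do not say so. They are silent on what labels and request forms carry, and the case report form (973CLD) and monitoring plan (935CLD) are separate documents not available here. The sentence also stands in a section on early termination, which suggests a general description of the trial and not a decision about pathology. This stands: what can be said is that masking of histology is excluded in terms and nowhere planned.

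A reader might also infer from the near-threshold example that a handful of calls decides this trial. At the plan's own effect that is not so, as the seven-call figure shows. Any test has a knife-edge near its threshold. Nor do the documents give a rate of borderline diagnoses or any evidence of reader bias.

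Nor do the documents show that pathology is the only step that could be masked. Section 2 says that Aer-O-Scope video is digitally recorded, and the analyst could also be masked.

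Finally, the gain is limited. The same unmasked endoscopist performs both passes and decides what is detected and sent to histology. The polyp miss rate (PMR) does not depend on histology and gains nothing. Lesions tattooed without removal may yield no specimen to code. These limits hold and bear on priority. They do not supply a reason for leaving the histology read open.

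**Conclusion.** The point holds as an avoidable risk of bias in the primary endpoint. The no-masking statement is broader than the reason given for it, and the plan does not mask the pathologist to device or pass. No bias is demonstrated, and its size cannot be estimated from the documents.

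The effect would be slight if the observed difference is near the planned 15 points. It could be decisive if the difference is nearer 9 points with about 108 adenomas per cohort. That count rests on the Section 7 assumptions and on treating lesions as independent in the plan's Z-test. Masking histology is a worthwhile and inexpensive improvement, but it does not cure the open-label detection step.

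**What to change.** 1. In Section 16, limit the no-masking statement to the endoscopist and the patient.
2. In Section 6.2, where specimen handling is described, add that each specimen carries the subject code and a random, non-chronological lesion code, and that device and pass are left off both the label and the pathology request. Numbering lesions in order of removal would not do: second-pass lesions would come last within each subject, and the number would partly reveal the pass.
3. State that the lesion-to-pass key stays on the case report form and is linked to histology only after the histology report is final.

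Because polyps are already sent one per specimen, this needs no extra reader or procedure and leaves sample size, significance level and power unchanged. The work is label and request-form wording at three sites, plus keeping the lesion key. The documents give no cost figure, so calling this inexpensive is a judgement. The report should state what masking leaves uncovered: endoscopist detection, the PMR, and tattooed lesions without a specimen.

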4 INVESTIGATIONAL DEVICE AND CLINICAL INVESTIGATION RISKS & BENEFITS

Risks	
The risks associated with the Aer-O-Scope Colonoscope are similar to those risks associated with conventional optical colonoscopy. As with all procedures related to colon screening, there are some associated risks. Risks associated with both colonoscopy and the Aer-O-Scope Colonoscope may include but are not limited to the following:
 
 • Lower digestive tract bleeding, • Colon perforation (that may result in inflammation of the peritoneum (peritonitis) or need for emergency medical treatment), • Excessive insufflation of the colon, • Erosion of the colon mucosa, • Sepsis • Venous thrombosis, • Vasovagal events, • Pain, • Ano-rectal Fissures, • Bloating and • Discomfort. 
Anticipated adverse device effects include bloating, flatulence mild in nature, ano-rectal fissures and minor discomfort. These symptoms are all transient and do not pose a potential risk to the subjects’ health.
 
The Aer-O-Scope Colonoscope system has been designed to minimize

--------------	---

Clinical Investigational Plan

Protocol ID	934CLD	Sponsor	GI View Ltd.
Revision	03	Investigational Device	Aer-O-Scope® Colonoscope System

	these adverse effects.

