Protocol ID	934CLD	Sponsor	GI View Ltd.
Revision	03	Investigational Device	Aer-O-Scope® Colonoscope System

	
study. When a patient is removed from the study, a final physical examination must be performed. Subjects removed from the study because of an adverse event will be followed-up until the adverse event has resolved.
 
Additional reasons for removing a patient from the study:
 
 1 Subjects who express a desire to withdraw from the study. 2 Any medical condition that, in the opinion of the investigator, warrants discontinuation from the study for the safety of the patient. 3 Poor colonic bowel cleansing that prevents proper visualization and intubation of the colon. 4 A large (≥20mm) polyp removal during first pass colonoscopy with a conventional colonoscope 5 Use of clips during first pass colonoscopy with a conventional colonoscope
Point of Enrollment	
Subjects will meet with the physician or physician appointed representative (such as a clinical coordinator) and be given ample opportunity to read and review the provided informed consent form and will be asked to sign prior to the beginning the bowel cleansing regimen. Subjects will be given the opportunity to ask the physicians questions prior to signing the informed consent. Subjects unable to sign prior to the day of procedure will be asked to sign the patient informed consent prior to entering the procedure room. A signed copy of the form will be provided for each patient.

Duration	
This multi-center, multi-national study is expected to last no longer than twelve (12) months. Each subject will be enrolled, undergo Aer-O-Scope Colonoscopy and conventional colonoscopy and be followed 24-48 hours via telephone post procedure. Subjects undergoing therapeutic interventions will be followed until the final histological results and only then will be terminated from the study.

Number of Subjects	
This study will include a total of 310 subjects in three (3) sites. Each site will study up to between 100 and 110 subjects (depending on the number of sub-investigators undergoing training). Subjects will be enrolled over a three (3) month period at each site and will undergo procedures over a three (3) month period at each site.

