6.4 Procedures

Procedures	
Subjects indicated for screening, diagnostic (for minor complaints such as rectal bleeding or minor abdominal pain) or polyp surveillance colonoscopy will meet with the physician or clinical coordinator prior to the procedure for a standard pre-procedure evaluation. Following a preliminary evaluation of eligibility, the patient will be informed of the clinical study and offered the opportunity to participate if he/she is an acceptable candidate. Should the subject agree to join the study, they will be provided a copy of the patient informed consent form and provided ample time to review the form. The point of enrollment will be upon signing the patient informed consent form. Subjects who sign the consent form but do not undergo any procedure will be recorded as screen

-------------------	---

Clinical Investigational Plan			
Protocol ID	934CLD	Sponsor	GI View Ltd.
Revision	03	Investigational Device	Aer-O-Scope® Colonoscope System

	
failures on a separate log, and removed from the enrollment roster.
 
The duration of this multi-national study is expected to be twelve (12) months, three (3) months per site. Each enrolled subject will participate for up to seven (7) days which will include the day of the informed consent signature, the bowel preparation and the day of procedures (Aer-O-Scope Colonoscopy and colonoscopy) with a 24-48 hour follow-up period.
 
Up to 200 subjects will be enrolled in the USA and up to 110 subjects will be enrolled in Israel with a total of up to 310 Subjects overall.

--	--

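### Primary safety endpoint 1.2 has no observation window, and the only post-procedure contact scheduled for every subject is a 24-48 hour call, so it could be declared met with no active enquiry about later events

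*Combined protocol and SAP*

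**What the plan says.** Primary objective 1.2 in the synopsis (Section 1.5) is to show that the device is safe. The matching endpoint reads "No serious adverse events or serious adverse device effects using the Aer-O-Scope Colonoscope System". No start, end or length of observation is attached to it.

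Follow-up is described in several places:

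- Section 16, Follow-Up: "Patients will be followed up 24-48 hours post procedure via telephone by the clinical coordinator at each site". The next sentence adds: "Patients who undergo therapeutic interventions will only be terminated from the study upon receiving the histology results".
- Section 6.3, Duration, repeats the 24-48 hour telephone follow-up and says: "Subjects undergoing therapeutic interventions will be followed until the final histological results and only then will be terminated from the study".
- Section 6.4 sets a limit for everyone: "Each enrolled subject will participate for up to seven (7) days which will include the day of the informed consent signature, the bowel preparation". The same span also covers the procedure day and the 24-48 hour follow-up.
- Section 8 makes the site coordinator responsible for seeing that the 24-48 hour calls are made. It lists no later call.
- Section 6.3, Withdrawal, requires a final physical examination for subjects who are removed, and adds: "Subjects removed from the study because of an adverse event will be followed-up until the adverse event has resolved".

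Section 14 defines an adverse event as one arising during the study. Recording starts at consent and no end is given. Section 4 lists the risks, among them "Lower digestive tract bleeding", perforation with possible peritonitis, sepsis and venous thrombosis. It gives no time to onset for any of them.

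**The concern.** A zero-event endpoint depends directly on how long one looks. A single event changes the result, and a shorter window makes success easier. Here the window is undefined, and for a subject without an intervention the schedule ends with a call one to two days after two colonoscopies in one session. The plan gives no reason why that interval is long enough to judge the serious risks it lists.

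A statement at the end that no serious event occurred would then partly reflect when the trial stopped asking. The same gap affects the safety board, which can review only what is reported to it.

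**Working it through.** **1. Is there a figure to reproduce?** No. Section 7 attaches no rate, precision or power to the safety endpoint. The check is a comparison of the text, followed by an illustration with assumed rates.

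**2. What each subject gets after the procedures, as written**

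| Subject | Scheduled contact | After that contact |
|---|---|---|
| No intervention | Call at 24-48 hours | Nothing scheduled |
| Intervention | Call at 24-48 hours | In study until histology; no date, no safety enquiry |
| Removed from the study | Final physical examination | If removed for an adverse event, followed until it resolves |

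The last row would not detect a new late event in a subject who completed the study.

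**3. Do the exit rules agree?** Sections 6.3 and 16 keep intervention subjects until histology, with no upper limit. Section 6.4 limits each enrolled subject to seven days. Both hold only if histology always arrives inside that span, and the plan gives no turnaround time. The seven days also include consent and bowel preparation, so they are not seven days of observation after the procedure.

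**4. When does recording stop?** Section 14 gives a start and no end. If the study period means the subject's own participation, an event after exit falls outside the definition. If it means the whole trial, the event would count, but no step is specified that would find it.

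**5. Illustration**

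Inputs from the documents: N = 310 subjects (Section 6.3); 50% of subjects with an adenoma (Section 7). Applying the 50% to all 310, training cases included, gives 310 x 0.5 = 155 with an adenoma and 155 without.

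Assumed: r, the rate per subject of serious events first appearing after the call, at 0.2%, 0.5% and 1%. None of these is in the documents.

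Formula: P(at least one late event among n unobserved subjects) = 1 - (1 - r)^n.

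| r | n = 155 | n = 310 |
|---|---|---|
| 0.2% | 1 - 0.998^155 = 27% | 1 - 0.998^310 = 46% |
| 0.5% | 1 - 0.995^155 = 54% | 1 - 0.995^310 = 79% |
| 1% | 1 - 0.99^155 = 79% | 1 - 0.99^310 = 96% |

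The n = 155 column assumes that subjects with an adenoma are effectively observed until histology and that all others leave at the call. The n = 310 column assumes that nobody is actively observed after the call.

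**6. What zero events would show.** With 0 of 310, the exact one-sided 95% upper bound is 1 - 0.05^(1/310) = 0.96%. It applies to events recorded within the window. If only half of all serious events fell within it (an assumption), the bound on total risk would be 0.96% / 0.5 = 1.92%.

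**The case against.** The strongest reply is that the plan is not blind after 48 hours. Intervention subjects remain in the study until histology. Section 14 requires moderate to serious events to be recorded from consent, serious events to reach the sponsor within 24 hours, and the safety board to review all adverse events. An event reported before exit would therefore be captured. Call content may also be specified in the case report form or the separate monitoring plan, which are not among these documents. This stands in part: what is missing is active enquiry and a defined end, not all capture. It does not help a subject without an intervention, who has nothing scheduled after the call.

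Three stronger readings are tempting and are not supported:

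- **That everyone is out by day seven.** Section 6.4 alone suggests this. Sections 6.3 and 16 contradict it for intervention subjects. The defect is the unreconciled conflict.
- **That the window is shown to be shorter than the risk period.** Section 4 gives no onset times. That some of the listed events would first present after 48 hours is plausible, but here it is an assumption.
- **That 46% to 96% is the size of the problem.** That range treats all 310 subjects as unobserved, although intervention subjects are retained longer.

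It is also fair to object that the assumed rates drive the probabilities. A single rate for all subjects ignores any difference in risk between those with and without an intervention. The rates count any late serious event after the tandem session, whereas the endpoint refers to events with the Aer-O-Scope.

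**Conclusion.** The point holds on the text alone in three respects: endpoint 1.2 has no observation window, the 24-48 hour call is the only post-procedure contact scheduled for every subject, and the exit rules in Sections 6.3 and 16 conflict with Section 6.4. The plan as written allows the primary safety endpoint to be declared met with no active enquiry about anything after the call.

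The size is conditional. It rests on the assumption that some serious events first present after 48 hours, and on assumed rates of 0.2% to 1%. Under those, the chance of at least one late event outside observation runs from 27% to 79% with about 155 subjects unobserved, and from 46% to 96% with all 310. The 155 is approximate and not a strict floor: subjects with non-adenomatous polyps removed would also stay until histology, and the plan gives no figure for them.

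This should be corrected. It limits what a safety conclusion can claim and does not affect the adenoma miss rate comparison.

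**What to change.** 1. State the observation window for endpoint 1.2 in Section 1.5, and give the matching end of adverse-event recording in Section 14.
2. Keep the 24-48 hour call and add one structured telephone enquiry about serious adverse events and adverse device effects, for every subject, at a fixed later time agreed with the safety board. The documents do not determine that time. The histology contact may serve if it falls on or after it and includes the same questions.
3. Reconcile Sections 6.3, 6.4 and 16 so that the participation limit and the histology rule agree.

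The cost is a short amendment and about 310 brief calls by the existing coordinators, with no added visit or procedure. Subjects close out slightly later, and the serious adverse event count may be less favourable.
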